#### 7.1. The severity of adverse events is characterized as follows

Mild: Any symptom of which the subject is aware, but which is easily tolerated.

**Moderate:** Any symptom which is discomforting enough to cause interference with a volunteer's usual activity.

**Severe:** Any symptom which causes a volunteer's inability to perform usual activity For all AEs, information will be obtained to determine causality.

The causal relationship between the investigational caffeine product and the AE will be characterized according to the following:

**Not related** – there is not a reasonable possibility that the study drug caused the AE.

**Unlikely** – suggests that only a remote connection exists between the study drug and the event. Other conditions, including concurrent illness, progression or expression of the disease state or reaction to concomitant medication, appear to explain the AE.

**Possible** – suggests that the association of the AE with the study drug is unknown, however the event is not reasonably supported by other conditions.

**Probable** – suggests that a temporal sequence of the AE with drug administration exists and, in the Investigator's clinical judgment, it is likely that a causal relationship exists between the drug administration and the AE, and other conditions (concurrent illness, progression or expression of the disease state, or concomitant medication reactions) do not appear to explain the AE.

Events where a causal relationship is classified as probable or possible will be regarded as related.

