#### **Risks**

There is a risk of participants experiencing side effects of caffeine such as palpitations, high blood pressure, gastrointestinal discomfort, insomnia and anxiety

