#### Criteria for stopping the trial or discontinuation of study intervention

28.02.2025

Individual subjects dosing will be stopped immediately if clinically relevant allergic reaction/ hypersensitivity occurs which needs medical intervention.

- 1. Dosing will be stopped if liver enzymes increases > 3 x normal range
- 2. Dosing will be stopped if conjugated bilirubin increases > 1.5 x normal range
- 3. Dosing will be stopped if serum creatinine increases > 1.5 x normal range
- 4. Dosing will be stopped if subjects suffer from a drug related (assessed as possibly or probably) and clinically relevant AE of moderate or severe intensity.
- 5. Any clinically significant values outside the reference ranges with major deviation and/or possible pathological relevance in physical examination, biochemical examination, hematology, vital signs measurements, electrocardiogram (ECG), and urinalysis.
- 6. Patients with AUDIT score > 8.

A volunteer can decide to withdraw from study participation at any time, for any reason, specified or unspecified, and without penalty or loss of benefits to which the subject is otherwise entitled. In this case, the subject must immediately contact the investigator and state that he is leaving the study.

Reasons for the withdrawal of the study (AE, ineffective treatment, inability to comply with the study requirements etc.) will be sought, if the patient is willing to provide that information. They will be made aware that their decision will in no way affect their treatment, and that they will be free to withdraw from study at any time. To respond to questions and record complaints during the study, contact details of two investigators will be provided to the study participants. Patient can be withdrawn from the study upon the principal investigator's decision to terminate the study, based on study compliance and adverse reactions development such as low rates of compliance, complications, or inability to tolerate the medication etc.

28.02.2025

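### The causality categories in Protocol section 7.1 have no place for an adverse event with both a plausible drug link and a plausible other cause, and leave it out of 'related'

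*Protocol*

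**What the plan says.** Section 7.1 of the Protocol defines four categories for the causal relationship between an adverse event (AE) and the caffeine product:

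- *Not related*: "there is not a reasonable possibility that the study drug caused the AE".
- *Unlikely*: the rating "suggests that only a remote connection exists between the study drug and the event". A second sentence adds: "Other conditions, including concurrent illness, progression or expression of the disease state or reaction to concomitant medication, appear to explain the AE".
- *Possible*: the rating "suggests that the association of the AE with the study drug is unknown, however the event is not reasonably supported by other conditions".
- *Probable*: there is a time sequence, in the investigator's judgement "it is likely that a causal relationship exists between the drug administration and the AE", and other conditions do not seem to account for the event.

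The section then reduces the four to two: "Events where a causal relationship is classified as probable or possible will be regarded as related".

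Two later parts of the Protocol use the result. The listing described in section 4.8 shows relationship to study drug for every event. Criterion 4 under the stopping criteria in section 7.7 reads: "Dosing will be stopped if subjects suffer from a drug related (assessed as possibly or probably) and clinically relevant AE of moderate or severe intensity". The CRF (Annexure 1C) offers the same four categories as tick boxes and no others.

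**The concern.** The two ends of the scale apply different tests. *Not related* asks whether the drug could reasonably have caused the event. *Possible* and *Probable* also ask whether anything else could have. An event can pass the first test and still be barred from both related categories because a second explanation exists. Two plausible causes are common in practice, and the scale has no defined place for them.

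Side effects of caffeine are a secondary objective (section 2.2), and section 3 states the aim of showing that the intervention is safe. If assessors handle such events differently, or all move them out of the related group, the recorded relationship loses meaning. An individual participant may then not meet criterion 4 because of how a definition is worded.

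**Working it through.** No arithmetic applies. The check sets the definitions side by side and tests each combination of drug link and other explanation against them.

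**Step 1. What each category requires (section 7.1).**

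| Category | Drug link required | Other explanation | Regarded as related |
|---|---|---|---|
| Not related | no reasonable possibility | not mentioned | no, by implication |
| Unlikely | remote only | appears to explain the event | no, by implication |
| Possible | unknown | must not reasonably support the event | yes |
| Probable | time sequence, and causation judged likely | must not appear to explain the event | yes |

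The Protocol states only which categories are related. That the other two are not related follows from this but is not written out.

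**Step 2. Every combination against those requirements.**

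| Drug link | No other condition explains the event | Another condition plausibly explains the event |
|---|---|---|
| No reasonable possibility | Not related | Not related |
| Remote | first sentence of Unlikely met, second not | Unlikely |
| Unknown but plausible | Possible | **none** |
| Likely | Probable | **none** |

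The two bold cells are the point at issue. In both:

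- *Possible* and *Probable* fail on their clauses about other conditions.
- *Not related* fails because a reasonable possibility exists.
- *Unlikely* fails because the link is more than remote.

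In *Probable* the clause about other conditions is joined to the judgement of likelihood by 'and', so a confident judgement of causation does not override it.

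**Step 3. What an assessor can do.** The CRF has boxes for non-related, unlikely, possible and probable, and none for an event that fits no definition. One must be ticked. *Unlikely* is the only category whose text accepts another explanation, so it is the most probable default. An assessor who ticks *Possible* instead goes against its wording, and ratings may then differ between assessors.

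**Step 4. Whether the case will arise.** Section 6.1 names "side effects of caffeine such as palpitations, high blood pressure, gastrointestinal discomfort, insomnia and anxiety". Each of these can have causes other than caffeine. The inclusion criteria (section 4.3.1) refer to type 2 diabetes and oral antidiabetic drugs, section 5.1 has comorbid diabetes and hypertension managed in routine care, and section 5.5 records concomitant medication monthly. Raised blood pressure in a participant with hypertension is one plain example.

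**Step 5. What the category controls.**

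| Item | Depends on the section 7.1 category? |
|---|---|
| Relationship shown for each event (4.8) | yes |
| Stopping criterion 4 (7.7) | yes |
| Collection of AEs (7.4) | no |
| All-event listing and % of participants with events (4.8) | no |
| Serious adverse event reporting (7.3) | no |

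**Step 6. Why no count is given.** A count of affected events would need the number of true caffeine reactions, the share with a plausible other cause, and the share of those that assessors place outside *Possible* and *Probable*. The Protocol gives none of the three.

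**The case against.** The strongest reply has three parts.

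**The definitions leave room for judgement.** A comorbidity that is merely present does not have to support or explain the event. New insomnia after starting tablets in someone with long-standing anxiety can still be judged unexplained by the anxiety. This stands, and it narrows the problem to events where the alternative is convincing. It does not close the gap: once the assessor finds both causes plausible, no definition fits.

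**The text does not send such an event to *Unlikely*.** A reader might infer that it is scored *Unlikely* by rule. The documents do not support that, because *Unlikely* also requires a merely remote connection. The defect is a missing category, and *Unlikely* is only the likely default.

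**The trial's safety picture does not rest on this label.** A reader might infer that the safety conclusion is biased towards safe. That is not shown:

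- Section 4.8 plans descriptive safety results, lists every event and gives the percentage of participants with events. It states no comparison of related-event rates.
- Assessment is blinded against placebo (section 4.7), so all-event figures can be compared by arm whatever the category.
- Serious events are reported regardless of causality, and the data safety monitoring board evaluates all adverse events (section 7.3).
- Expedited reporting of serious unexpected reactions refers to Good Clinical Practice definitions (section 7.4) and does not cite the section 7.1 categories.
- Criterion 5 and termination for an adverse event, both in section 7.7, carry no causality condition.

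All of this stands and limits the consequence. None of it makes the four definitions consistent or alters the direct dependence of criterion 4 on them.

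**Conclusion.** The point holds as a defect in a stated rule. The four categories are not exhaustive, and the route to 'related' conflicts with the reasonable-possibility test in the same section. An event with a plausible drug link and a plausible other cause meets no definition and, as written, cannot be regarded as related.

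The effect is on the relationship recorded for each event and on whether criterion 4 is met. Events are not lost from collection, listing or serious-event reporting. The size cannot be expressed as a number of events or participants; any such figure would be a product of assumed inputs. The conclusion rests on reading the definitions literally and on the clauses about other conditions being binding, as their wording indicates. That most such events would end up as *Unlikely* is an expectation about assessors, not something the Protocol states.

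**What to change.** 1. Reword *Possible* and *Unlikely* in section 7.1 so that every event fits exactly one category, and so that an event with a reasonable possibility of drug causation is not kept out of 'related' solely because another explanation also exists. Bring the clause on other conditions in *Probable* into line.
2. Print the same definitions beside the causality boxes in the CRF (Annexure 1C).
3. Have the investigators reconcile section 7.1 with criterion 4 in section 7.7, which depends on these categories. What the stopping rule should be is for them to decide.

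The change is best made before any event is classified, since later reclassification is harder, especially where a code has been broken after a serious event. The cost is a protocol wording change and a short CRF note, with no new data or procedures. There is a real downside: more events in both arms may be classed as related, and more participants may meet criterion 4 as it is now worded. That is why step 3 should accompany step 1.

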#### 7.2. Outcome

The outcome of the adverse event will be classified according to the following definitions:

**Recovered / resolved:** the event has resolved (no further symptoms are present, and no treatment is being received by the subject).

Recovered / resolved with sequelae: the event has resolved but lingering effects may be present.

**Fatal** / **life threatening:** the subject died as a result of the event. This code should only be used for the event that caused the death, not any event that was present at the time of the subject's death.

28.02.2025

**Unknown:** will be used in the event that the subject is lost to follow-up and no reliable data can be obtained.

All observed AEs will be reported as described in the following sections.

Medically qualified investigators will obtain appropriate information to determine the outcome of the AE and to assess whether it meets the criteria for classification as a Suspected Unexpected Serious Adverse Reaction (SUSAR) requiring immediate notification.

The codes can be accessed all 24hrs and in the event of a SAE when the code of that patient will be broken.

#### 7.3. Reporting

Mechanisms for direct reporting of probable adverse events to investigator by patients will be in place (via direct contact). In addition, during evaluation visits probable adverse events, if any will be noted and relevant volunteers will be investigated in detail to determine any association with the drug.

Any serious adverse event as defined in GCP guidelines will be reported to the National ADR monitoring center in the Department of Pharmacology, Faculty of Medicine, Colombo within 24 hours and the Ethics Review Committee as soon as possible. Data Safety Monitoring Board (DSMB) will evaluate all data and adverse events, if any at intervals during the trial as stipulated by the DSMB.

## 7.4. Reporting Period

All AEs, whether serious or non-serious, observed and/or spontaneously reported, beginning from the time the informed consent is signed and dated, are collected on the source document.

All adverse drug reactions that are both serious and unexpected (SUSAR) will be reported.

The researcher will report any serious unexpected adverse drug reaction (as defined in the Good Clinical Practices (GCP) Guidelines in CIOMS-I format as soon as possible, but no later than

28.02.2025

fifteen calendar days after the sponsor is made first aware of such reaction to the Ethics Review Committee and the investigators participating in the clinical trial.

Any fatal or life-threatening serious unexpected adverse drug reaction will be reported by the researcher to the Ethics Review Committee and the investigators participating in the clinical trial as soon as possible, but not later than seven calendar days

## 7.5. Investigation

Any adverse events/reactions will be investigated in detail.

## 7.6. Management

In the event of an adverse event or adverse reaction such events will be managed as soon as possible under the direct supervision of a Consultant Physician with no cost to the volunteer. After the research is completed, the volunteers can reach the investigators for any concerns about health.

## 7.7. Termination of Study and withdrawal from the study

The principal investigator will terminate a volunteer participant from the trial in the following cases. In such an event, Principal investigator will inform the participant about termination of the study and the reason for termination.

- Occurrence of an adverse event which does not justify continuation of the study
- Protocol violation which jeopardizes the performance of the study

If a volunteer is not adhering to the proposed medication protocol a detailed discussion will be held to understand the reason for non-adherence to determine whether it is tablet related or due to another reason such as forgetfulness or does not want to continue with the medication on personal preference which is unrelated to the product. No intimidation or force would be used to improve compliance if the participant refuses to provide any information

#### Criteria for stopping the trial or discontinuation of study intervention

28.02.2025

Individual subjects dosing will be stopped immediately if clinically relevant allergic reaction/ hypersensitivity occurs which needs medical intervention.

- 1. Dosing will be stopped if liver enzymes increases > 3 x normal range
- 2. Dosing will be stopped if conjugated bilirubin increases > 1.5 x normal range
- 3. Dosing will be stopped if serum creatinine increases > 1.5 x normal range
- 4. Dosing will be stopped if subjects suffer from a drug related (assessed as possibly or probably) and clinically relevant AE of moderate or severe intensity.
- 5. Any clinically significant values outside the reference ranges with major deviation and/or possible pathological relevance in physical examination, biochemical examination, hematology, vital signs measurements, electrocardiogram (ECG), and urinalysis.
- 6. Patients with AUDIT score > 8.

A volunteer can decide to withdraw from study participation at any time, for any reason, specified or unspecified, and without penalty or loss of benefits to which the subject is otherwise entitled. In this case, the subject must immediately contact the investigator and state that he is leaving the study.

Reasons for the withdrawal of the study (AE, ineffective treatment, inability to comply with the study requirements etc.) will be sought, if the patient is willing to provide that information. They will be made aware that their decision will in no way affect their treatment, and that they will be free to withdraw from study at any time. To respond to questions and record complaints during the study, contact details of two investigators will be provided to the study participants. Patient can be withdrawn from the study upon the principal investigator's decision to terminate the study, based on study compliance and adverse reactions development such as low rates of compliance, complications, or inability to tolerate the medication etc.

28.02.2025

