#### Laboratory investigations

Serum fasting plasma glucose, Lipid profile, Liver enzymes will be done to assess the
baseline fasting blood glucose for recruitment into the study to comply with inclusion
criteria. Serum HCG will be tested for female participants to exclude pregnancy.
Abdomen ultrasound scan will be performed to assess eligibility to the study.

28.02.2025

After recruitment baseline testing will be done for HbA1c, serum Insulin level, fasting
plasma glucose, Lipid profile, Liver enzymes. Serum creatinine, full blood count, serum
electrolytes and urine analysis will be done for safety assessments.

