#### Collection of blood samples

• Table 1 summarizes the blood sample collection. The investigations will be done at the North Colombo Teaching hospital which is an accredited laboratory. These tests are required to assess the efficacy and safety of the medications in an objective manner.

Table 1: Summary of Blood Sample Collection

Day	Blood volume	Investigations
Enrolment	6 ml	FBS, Liver profile  Lipid profile, Serum HCG (Female participants only)
Allocation Visit - Beginning of 1 st Month	6 ml	FBS Serum HbA1c Fasting serum insulin

28.02.2025

		Lipid profile, Liver profile, Total bilirubin
		Serum creatinine
		FBC
		Serum electrolytes
3 rd month and 6 th month	6 ml	FBS
		Serum HbA1c
		Fasting serum insulin
		Lipid profile, Liver profile, Total bilirubin
		Serum creatinine
		FBC
		Serum electrolytes

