## 5. Intervention, Monitoring of compliance to treatment

Caffeine tablets and placebo tablets required for the trial would be sourced from Nutricost, a U.S.-based company that specializes in high-quality dietary supplements. Nutricost products are manufactured in GMP-compliant facilities and undergo third-party testing to ensure purity and consistency. The caffeine tablets specifically contain caffeine anhydrous, a dehydrated form of caffeine that provides a standardized and effective dosage and placebo are manufactured using starch ensuring that it is inert and does not affect the study's outcomes.

The study groups will receive one bottle on the day of allocation, and it will contain either caffeine tablets or placebo required for a month. The test group will receive the caffeine tablet while the control group will receive the placebo .Tablet bottles will be issued to participants according to their random number mentioned in the Case Report Form (CRF).

Patients will be asked to take the medication every day after dinner. Recommended dose and directions for use will be given verbally when dispensing the tablet pack, and written instructions will be clearly mentioned on the label of the bottle in Sinhala, Tamil and English. The patients will be asked to take the tablets home. At each monthly visit, the participants will be asked to bring tablet bottles with balance tablets, to count at the monthly visit to assess compliance. The required tablets for next month will be issued during this visit.

Participants who have < 80% compliance will be re-educated on the importance of daily administration of investigational product, as much as possible: with the overall aim to maintain  $\ge$  80% compliance over the study period.

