#### 5.5. Follow up assessment

The recruited patients will be advised to come for monthly assessments and will be asked to attend the nearest hospital, if they develop any complications and inform the study team of such incidence.

The degree of adherence to prescribed lifestyle changes and diet will be recorded at the baseline and monthly follow-up visits. Physical activity and alcohol consumption will also be monitored at the baseline and monthly follow-up visits.

Anthropometric measurements, physical examination and vital sign measurements (BP, HR, RR etc..) will be monitored at the baseline and each monthly visit. Details on concomitant medications will be recorded in monthly visits.

Liver profile, Lipid profile, Full blood count, Serum creatinine, fasting blood glucose, HbA1c, serum insulin, serum electrolytes and urine analysis and serum insulin will be investigated at the baseline, at 3 months and 6 months.

Fibro scan will be done at the baseline and after 6 months at the completion of the study.

The details of items which will be measured on every visit are described in Table 2.

Table 2: Summary of follow up

	Enrolment	Allocation 1	Subsequent visits							
TIME POINT		0	1 st	2 nd	3 rd	4 th	5 th	6 th		
			mont	mont	month	mont	month	mont		
			h	h		h		h		
ENROLMENT										
Eligibility screen	×									
Informed consent	×									
Allocation		×								
INTERVENTIO										
NS										
caffeine or		×	×	×	×	×	×			
placebo										
ASSESSMENTS										
Medical history	×	×	×	×	×	×	×	×		
taking										
AUDIT	×	×	×	×	×	×	×	×		
FFQ and IPAQ	×	×	×	×	×	×	×	×		

Height, weight			×	×	×	×	×	×
and waist								
circumference								
Blood pressure	×	×	×	×	×	×	×	×
Physical examination 	×	×	×	×	×	×	×	×
USS scan	×							
Fibro scan		×						×
FBG	×	×			×			×
Fasting serum insulin		×			×			×
HCG only female	×							
Serum HbA1c		×			×			×
Lipid profile	×	×			×			×
Liver enzymes	×	×			×			×
Total bilirubin	×				×			×
Serum creatinine		×			×			×
Serum electrolytes		×			×			×

FBC	×		×		×
UFR	×		×		×

28.02.2025

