# **Examination:**

General examination:	
Height(cm):	
Weight(kg):	
Waist Circumference(cm):	
BMI:	
Other	
Findings:	
CVS examination:	
Blood Pressure(mmhg):	
Heart Rate:	
Other	
Findings:	
Respiratory Examination:	
Respiratory rate:	
Other	
Findings	
rinanigs.	
Findings:	
rindings	
rindings	
Abdomen Examination:	

Randomized, Quadruple-blind, Placebo-controlled, Clinical Trial to determine the effects of Coffee (caffeine
supplementation on Hepatic Steatosis and Fibrosis in Metabolic dysfunction-associated Steatotic Live
Disease(MASLD)Version 1

Other Important		
Findings:		

e	estigations:	
	FBC:	
	Serum Electrolytes:	
er.	r Assessments:	
	AST (IU/L):	
	ALT (IU/L):	
	GGT (IU/L):	
	Total Bilirubin:	
	CAP Score:	
	LSM (Fibro scan):	
	FIB-4 Score:	
	US scan	
	Findings:	
	E'I	
	Fibro scan	
	Findings:	
ab	abolic Assessments:	
	Profile:	
	• Total Cholesterol (mg/dL):	
	Triglycerides (mg/dL):	
	• HDL (mg/dL):	
	• LDL (mg/dL):	

Blood glucose:	
•	Fasting Blood Sugar (FBS) (mg/dL): HbA1c (%): Fasting Serum Insulin:
Others:	rasting Serum hisumi.
•	Serum Creatinine: UFR:

28.02.2025

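### The bilirubin stopping rule names a fraction that the schedule and CRF do not name, and the adverse event outcome codes have no place for an ongoing event

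*Protocol*

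**What the plan says.** **Bilirubin.** Section 7.7 lists six numbered criteria for stopping an individual's dosing. Criteria 1 to 3 set fixed laboratory limits, on liver enzymes, conjugated bilirubin and serum creatinine. The second is "Dosing will be stopped if conjugated bilirubin increases > 1.5 x normal range". Criterion 5 is a general clause covering "Any clinically significant values outside the reference ranges with major deviation and/or possible pathological relevance", and it extends to biochemistry.

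Table 1 (section 4.6) lists "Lipid profile, Liver profile, Total bilirubin" at allocation and at months 3 and 6. Table 2 (section 5.5) has a row for "Total bilirubin" and a separate row for liver enzymes. The laboratory text of section 4.6, which ends "electrolytes and urine analysis will be done for safety assessments", names no bilirubin. Nor does the follow-up text of section 5.5, which begins its list with "Liver profile, Lipid profile, Full blood count, Serum creatinine, fasting blood glucose". The liver section of the CRF (Annexure 1C) has single fields for AST, ALT, GGT and "Total Bilirubin".

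**Adverse event outcome.** Section 7.2 defines four codes: recovered, recovered with sequelae, fatal/life-threatening, and unknown. The CRF offers the same four as tick-boxes without the definitions. Section 4.8 plans a listing of all adverse events that shows start and end dates, seriousness and outcome, among other items.

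**The concern.** A stopping rule with a fixed limit works only if its analyte is measured and someone can later show whether the limit was crossed. Conjugated bilirubin appears in the rule and nowhere else in the protocol. If the laboratory panel does not report it, the 1.5-fold limit cannot be applied. If the panel does report it, the CRF has no field to show whether the rule was met or followed.

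The outcome codes are a separate fault in the same safety system. Section 6.1 names insomnia, anxiety, palpitations and high blood pressure as caffeine risks. Such an event may well still be present at a monthly visit, or when dosing is stopped under criterion 4. An investigator who follows section 7.2 exactly then has no correct code. One who reads only the CRF label may record a survived life-threatening event under a code that section 7.2 defines as death. Those entries feed the listing in section 4.8.

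**Working it through.** No statistical calculation applies. The check sets the texts side by side.

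**1. Are the fixed laboratory stops matched by the schedule and the CRF?**

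| Criterion | Analyte in the rule | Named in Tables 1 and 2 | CRF field |
|---|---|---|---|
| 1 | Liver enzymes | Yes (liver profile / liver enzymes) | AST, ALT, GGT |
| 2 | Conjugated bilirubin | No; total bilirubin only | No; total bilirubin only |
| 3 | Serum creatinine | Yes | Yes |

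One of the three fixed limits has no matching entry. Of the four liver blood analytes on the CRF, none is the conjugated fraction.

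**2. Could the liver profile include the fraction?** It could, because its contents are not stated. The wording leans the other way: Table 1 lists total bilirubin next to the profile as a separate item, and Table 2 calls the panel liver enzymes. The supportable statement is that measurement is not assured, not that it will not happen.

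**3. When could the rule act?** Post-baseline liver bloods are scheduled at 2 visits, months 3 and 6. Section 5 says of each monthly visit "The required tablets for next month will be issued during this visit", and Table 2 last marks tablets at month 5. By month 6 there is no further dosing to stop. Month 3 is therefore the only scheduled sample on which criterion 2 could stop dosing. The same timing applies to criteria 1 and 3, so it is not a fault of the bilirubin wording, but it leaves little room for a missed measurement.

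**4. Which outcome code fits an ongoing or a survived life-threatening event?**

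| Code in section 7.2 | Condition in its definition | Fits an ongoing event? | Fits an ongoing life-threatening event, participant alive? |
|---|---|---|---|
| Recovered | Resolved, no symptoms, no treatment | No | No |
| Recovered with sequelae | Resolved, lingering effects possible | No | No |
| Fatal/life-threatening | Death caused by the event | No | By label only |
| Unknown | Lost to follow-up, no reliable data | No | No |

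For an ongoing event, 0 of 4 codes fits. A life-threatening event that later resolves belongs under one of the first two codes, yet the label of the third invites the tick. Adverse events are asked about at each of 6 monthly visits, so the situation can arise repeatedly.

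**5. Can the facts be recovered elsewhere?** The listing in section 4.8 is to show start and end dates and seriousness. In the CRF text available, the adverse event section asks for degree, relation to treatment, outcome, action taken and a free-text summary. It shows no field for event dates or for seriousness. Recovery would rest on the source documents and the free text.

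**The case against.** **On bilirubin.** Clinicians stop dosing from the laboratory report, not from the CRF, and what a liver profile contains is a matter for the laboratory. Other safeguards act on the same participants: criterion 1 on enzymes, criterion 4 on related moderate or severe events, criterion 5 on any significant value, and a data safety monitoring board that includes a hepatologist. The CRF also has free-text findings and a discontinuation box.

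Much of this stands. A raised total bilirubin can stop dosing under criterion 5, so participants are not unprotected. But criterion 5 is a judgement, whereas the protocol set a fixed limit. Criterion 1 does not act on a bilirubin rise without an enzyme rise. A missing CRF field does not disable the rule, but it prevents a structured check that the rule was followed.

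**On the outcome codes.** An event without an end date can be read as ongoing, outcomes can be coded once known, and section 7.2 restricts the third code to the event that caused death. In a single-centre trial of 110 participants with expedited reporting, a survivor is unlikely to be mistaken for a death for long.

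This narrows the problem. If codes are updated at later visits, the gap is mainly events unresolved at the participant's last contact. The end-date route is weak because the CRF text shows no date field. The restriction on the third code is in section 7.2 and not on the form the investigator completes.

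The CRF was read from a converted PDF with damaged headings, so absent fields should be confirmed on the original form.

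**Conclusion.** Both parts hold as written. Criterion 2 is one of three fixed laboratory stops and the only one whose analyte is neither named in the schedule nor given a CRF field. The consequence is limited: where the panel omits the fraction, a fixed 1.5-fold stop becomes a judgement under criterion 5. None of the four outcome codes covers an ongoing event, and one code's label and definition disagree. The outcome column of the adverse event listing would be wrong for the events concerned, although source documents and free text could restore the facts.

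The number of participants affected cannot be estimated from the protocol. The conclusion assumes that the liver profile is not defined in a document outside the protocol and that the CRF has no fields beyond those visible. The change should be made for safety monitoring and data quality.

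**What to change.** **Criterion 2 (section 7.7), one of two options:**
- Restate it on total bilirubin, which is already scheduled. Total bilirubin includes the unconjugated fraction, so a 1.5-fold limit on the total is not the same rule; the limit needs clinical confirmation. No test is added.
- Keep conjugated bilirubin, add direct bilirubin to the existing month 3 and month 6 samples, name it in Tables 1 and 2, and give it a CRF field. This uses blood already drawn and adds one analyte.

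**Outcome codes (section 7.2 and CRF):**
- Add a not-recovered/ongoing code.
- Make fatal a code of its own, with the present definition.
- Remove life-threatening from outcome and record it under seriousness, which the listing in section 4.8 already plans to report. If the original form has no seriousness field, add one.

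The cost is a wording amendment to sections 7.2 and 7.7 and to the CRF, plus Tables 1 and 2 if direct bilirubin is chosen. No visits are added.
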